6.3 PATIENT SETS ANALYSED

Treated Set (TS): All patients with at least one documented prescription of dabigatran etexilate or VKA.

Full Analysis Set (FAS): All patients from the Treated Set with main diagnosis non-valvular atrial fibrillation and who have at least one evaluable efficacy endpoint.

Matched group (MG): Patient cohort resulting from the 1:1 matching based on FAS.

Table 6.3: 1 Patient sets analysed

Class of endpoint	TS	MG
Primary and secondary endpoint		X
Safety endpoints	X	
Demographic/baseline	X	X

6.5 POOLING OF CENTRES

This section is not applicable because centre/country is not included in the statistical model.

6.6 HANDLING OF MISSING DATA AND OUTLIERS

Missing or incomplete AE dates are imputed according to BI standards (see “Handling of missing and incomplete AE dates”). All available data will be used in the data analysis. Drop-outs will be adequately reflected because of the underlying method (survival analysis). Missing values will be categorized as “Missing” and will not be imputed.

Outliers will not be excluded from analysis.

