7.4 Procedure for missing data

All available information will be used in the data analysis. Drop-outs will be duly considered in the main analysis by virtue of the methodology used (survival time analysis).

Missing values will be identified as such and no replacement is planned.

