Reasons for change 2:

After 6 months of site and patient recruitment it became evident that the targeted patient and site numbers will not be met and that recruitment time should be longer.

Therefore the planned patient number will be reduced to 1600 and site number to 800.

Recruitment time will be prolonged to 16 months (LPI December 2015), thus study duration will also increase. LPO is now planned for December 2016.

Other timelines will change accordingly.

CHANGE 3: ADAPT TIME SCHEDULE, SITE NUMBERS AND PATIENT NUMBERS

Section of the protocol: Statistics Section Determination of number of patients

It is planned to include a total of 4000 patients in this non-interventional, controlled, observational study (dabigatran etexilate: 2000 patients, VKA: 2000 patients).

Calculation of statistical power:

All analyses are purely exploratory by virtue of the non-interventional study design. On the following assumptions:

- 15% drop-outs /missing values after one year,
- 2000 dabigatran etexilate patients, 2000 VKA patients, with 66% of VKA patients with a matching partner in the dabigatran etexilate group (i.e. total number of patients in the 1:1 matched analysis is 2640)
- a persistence rate of 63% in the dabigatran etexilate group (cf. 1-year persistence with a 60-day permissible medication gap as reported by Zalesak ¹⁹)).

the power for a descriptive p value ≤ 0.05 in a 2-tailed test for the same persistence rates is as follows (dependent on the VKA persistence rate):

Assumed VKA persistence rate*	51%	53.8%	56.5%
Power	100%	99.7%	91.7%

* The calculations were performed with ADDPLAN6 and are based on survival time analysis test statistics and the endpoint variables "Time to permanent treatment discontinuation".

Was changed to:

It is planned to include a total of 1600 patients in this non-interventional, controlled, observational study (dabigatran etexilate: 800 patients, VKA: 800 patients).

Calculation of statistical power:

All analyses are purely exploratory by virtue of the non-interventional study design. On the following assumptions:

- 15% drop-outs /missing values after one year,
- 800 dabigatran etexilate patients, 800 VKA patients, with 66% of VKA patients with a matching partner in the dabigatran etexilate group (i.e. total number of patients in the 1:1 matched analysis is 1056)
- a persistence rate of 63% in the dabigatran etexilate group (cf. 1-year persistence with a 60-day permissible medication gap as reported by Zalesak (¹⁹)).

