the power for a descriptive p value ≤ 0.05 in a 2-tailed test for the same persistence rates is as follows (dependent on the VKA persistence rate):

Assumed VKA persistence rate*	51%	53.8%	56.5%
Power	97.8%	84.8%	61.1%

* The calculations were performed with ADDPLAN6 and are based on survival time analysis test statistics and the endpoint variables "Time to permanent treatment discontinuation".

Reasons for change 3:

After 6 months of site and patient recruitment it became evident that the targeted patient and site numbers will not be met and that recruitment time should be longer.

Therefore the planned patient number will be reduced to 1600 and site number to 800.

Observational Plan

Non-interventional study

Local Amendment

Local Amendment Number:	Local Amendment 2			
Country	Germany			
Date:	04. JAN 2016	 To be implemented only after documented approval of the IRB / IEC / Competent Authorities		
EudraCT No.:	n.a.	 To be implemented immediately in order to eliminate hazard – IRB / IEC / Competent Authority to be notified of change with request for approval		
BI Trial No.:	1160.218			
Investigational Product(s):	Pradaxa®	 Can be implemented without IRB / IEC / Competent Authority approval as changes involve logistical or administrative aspects only		
Title:	Drug persistence/adherence in patients being treated with Pradaxa® (dabigatran etexilate) or vitamin K antagonists (VKA) for stroke prevention in non-valvular atrial fibrillation (AF)			
Rationale for Local Amendment:	
After 15 months of patient recruitment 1050 / 1600 patients have been included until December 2015. For a meaningful data analysis and interpretation, the targeted patient number of 1600 patients should be met.
 
Therefore, recruitment time will be prolonged for one more year to 27 months (LPI December 2016), thus study duration will also increase. LPO is now planned for December 2017.
 
Other timelines will change accordingly.
 
In case 1600 patients will be included earlier, recruitment may be stopped before December 2016.
 
As this amendment is administrative and does not change the content or the nature of this non-interventional study, for readability reasons we refrain from changing every sentence in which site numbers, patient numbers or timelines are mentioned, except for the front page, study synopsis and statistics section.
			
Page 1 of 3				

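### Survival analysis reflects drop-outs adequately only if leaving the study is independent of stopping the drug, and no planned analysis varies that assumption

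*SAP*

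**What the plan says.** SAP 6.6 states: "Drop-outs will be adequately reflected because of the underlying method (survival analysis". Protocol 7.4 makes the same claim: "Drop-outs will be duly considered in the main analysis by virtue of the methodology used (survival time analysis". Both sections rule out imputation of missing values.

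The censoring rule is in SAP 5.1 and 7.4 and in Protocol 7.3. A documented treatment stop is an event. A patient who leaves the study early with no documented stop is censored at study termination. A patient who completes the study on treatment is censored the day after the last visit.

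The SAP gives no drop-out figure. The protocol's power calculation (section 7.5, carried over in Local Amendment 1, Change 3) assumes "15% drop-outs /missing values after one year".

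**The concern.** Kaplan-Meier estimates and the log-rank test need censoring that is independent of the event. Choosing survival methods does not make it so. Here the event is stopping the drug and the censoring is leaving the practice's follow-up, and the two may be closely linked. Continuation is recorded by the practice about every three months, without a pill count (Protocol 4.1.4 and 5.3). A patient who quietly stops and no longer attends is therefore censored and treated as if still at the average risk of stopping. Persistence is then overstated.

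The bias may also differ between arms. Protocol 1.1 describes INR checks at least every 3 to 4 weeks on VKA, and Protocol 1.2 says dabigatran needs no routine coagulation monitoring. An unrecorded stop could thus be more likely with dabigatran. That is an inference; neither document gives data on it.

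Comparing persistence is the primary objective, so at stake are both the 12-month estimates and the size of the difference.

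**Working it through.** **Inputs (Local Amendment 1, Change 3).** Dabigatran persistence at 12 months 63%; VKA persistence 51%, 53.8% or 56.5%; 1056 matched patients, 528 per arm; 15% drop-outs or missing values; two-sided 0.05; power "based on survival time analysis test statistics".

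**The plan's own figures first.** Take HR = ln(0.63)/ln(VKA rate), constant hazards, and independent drop-out reaching 15% at 12 months. Schoenfeld power is Φ(|ln HR|·√events/2 − 1.96).

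- VKA 51%: HR 0.686, 422 events, power 97.2% (stated 97.8%).
- VKA 53.8%: HR 0.745, 408 events, power 84.4% (stated 84.8%).
- VKA 56.5%: HR 0.809, 395 events, power 55.7% (stated 61.1%).

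The first two reproduce. The third does not under any two-sided variant tried (51.0% to 58.8%). That is a separate matter, and nothing below uses the power figures.

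**Effect of hidden stops.** Let f be the share of leavers who had in fact stopped when they left. Assume f is constant over time and the other leavers are independently censored. If 15% is the cumulative drop-out probability and all of it is leavers of unknown drug status, then

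true persistence = Kaplan-Meier estimate × 0.85^f.

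The documents give no value for f. A simulation with two million patients per rate agreed: with every leaver counted as stopped, 63% became 53.56% and 53.8% became 45.74%; with half counted, 58.09% and 49.58%.

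At f = 1:

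- Dabigatran: 63 × 0.85 = 53.55%.
- VKA: 51 × 0.85 = 43.35%; 53.8 × 0.85 = 45.73%; 56.5 × 0.85 = 48.025%.

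For hidden stops with dabigatran only, the difference vanishes when 0.63 × 0.85^f equals the VKA rate, so f = ln(VKA rate/0.63)/ln(0.85).

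Dabigatran minus VKA, in percentage points:

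| VKA rate | Assumed | f = 1 in both arms | f = 1, dabigatran only | f = 1, VKA only | Vanishing share, dabigatran only |
|---|---|---|---|---|---|
| 51% | 12.0 | 10.20 | +2.55 | 19.65 | 1.30 (above 1, not attainable) |
| 53.8% | 9.2 | 7.82 | −0.25 | 17.27 | 0.97 |
| 56.5% | 6.5 | 5.525 | −2.95 | 14.975 | 0.67 |

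**Reading of the 15%.** If it instead means the share of patients observed to leave, then under constant hazards 63% becomes 51.3% at f = 1, and the 6.5-point difference vanishes at f = 0.53. The table uses the milder reading.

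**Do the planned analyses vary the assumption?**

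- The Cox model on common support (SAP 7.4) changes the population and the adjustment. No change to the censoring is specified.
- The baseline table by premature study discontinuation (SAP 7.4) describes leavers but does not re-estimate persistence.
- The baseline comparison of patients without a Morisky score (SAP 7.5) needs strata of at least 200. Expected drop-out among matched patients is 0.15 × 1056 = 158 over the year, or 1056 × (1 − 0.85^0.5) = 82 by month 6. On these figures the study drop-out stratum would not reach the threshold.

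**The case against.** The plan is designed to record stops. Stop date, reason and later antithrombotic therapy are collected at visits 2 to 5, adverse events are followed for 30 days after treatment ends, and Protocol 6.2 expects anticoagulated patients to be seen at least quarterly. Stopping the drug is not meant to end participation. This stands: only undocumented stops cause bias, and no passage shows that leavers have stopped more often than others.

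The 15% is a protocol planning figure that mixes drop-outs with missing values and does not appear in the SAP. This stands too, so treating all of it as leavers is an assumption that gives an upper bound on this component.

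A reader might infer that the treatment conclusion is likely to reverse. The documents do not support that. If all leavers in both arms had stopped, dabigatran stays ahead in all three scenarios. A reversal needs hidden stops confined to dabigatran. Even then it is clear only at 56.5%, where the plan's stated power is lowest; it is marginal at 53.8% and impossible at 51%.

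The Cox sensitivity model conditions on covariates, so it needs only conditionally independent censoring. That is a weaker requirement, but its factors (the two risk scores, age, previous stroke and treatment) do not record whether a leaver had stopped.

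All analyses are declared descriptive (Protocol 7, SAP 7). That limits the consequence but does not make the sentence in SAP 6.6 true.

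**Conclusion.** The concern holds in a limited form. The claim in SAP 6.6 and Protocol 7.4 depends on an assumption that neither document states, that is doubtful for this endpoint, and that no planned analysis varies. Under the planning figures, hidden stops could overstate persistence by up to about 9.5 points with dabigatran (63 − 53.55) and about 7.7 to 8.5 points with VKA (51 − 43.35 to 56.5 − 48.025).

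These are bounds, not predictions. They rest on reading 15% as the cumulative probability of leaving with unknown drug status, and on assumed values of f. Equal hidden stopping in both arms shrinks the difference modestly. Only a strongly one-sided pattern removes it, and only in the two smaller-difference scenarios. It would go too far to say that survival analysis is the wrong method or that the primary comparison is invalid. The improvement is cheap and bears on the primary comparison.

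**What to change.** 1. Replace the sentence in SAP 6.6 (and align Protocol 7.4) with a statement that censoring of leavers without a documented stop is assumed independent of stopping treatment.
2. Report the number, timing and reason of study drop-out by arm and visit.
3. Add to the matched-cohort primary analysis a sensitivity analysis, labelled as a bound, that counts leavers without a documented stop as discontinued: in both arms, then in one arm at a time, with the share of leavers at which the difference vanishes.
4. Show deaths separately and do not count them as undocumented stops.
5. Include and report patients with no visit after visit 1, and state the event date used for them. SAP 5.1 starts the clock at the first visit, so a last-visit rule would give them time zero. The full analysis set requires at least one evaluable efficacy endpoint (SAP 6.3), so the plan should also say how these patients enter the matched cohort.

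The cost is a few reruns of the planned analysis on data already collected, and a deliberately pessimistic result that must be presented as a bound.

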6.7 BASELINE, TIME WINDOWS AND CALCULATED VISITS

The treatment with Pradaxa®/ VKA will be documented approximately every 3 months over a period of 12 months (in common control time points after approx. 3, 6, 9 and 12 months).

Baseline visit will include historical data/ registration and visit 1- initial examination.

Visit 2, 3, 4 and 5 will be labelled as retained from the eCRF. Final examination will include data collected at end of study examination.

7. PLANNED ANALYSIS

All analyses in this study are descriptive; results are to be interpreted in an explorative manner.

For categorical variables summary tabulations of the number and percentage within each category (with a category for missing data) of the parameter will be presented. For continuous variables N, mean, SD, minimum, median, maximum and number of missing values will be presented. To achieve a valid comparability of compliance (persistence and adherence) patients prescribed to dabigatran etexilate or VKA will be matched 1:1 based on the Exposure Propensity Score (PS) and caliper matching with caliper of width equal to 0.2xStandard deviation of PS.

The Propensity Score will be calculated based on a logistic regression model taking the choice of treatment as dependent variable and baseline characteristics as independent variables into account. All baseline variables with an a priori association to persistence and adherence will be included into the regression analysis.

These variables correspond to the potential cofounder variables for a comparative analysis.

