7.4 PRIMARY ENDPOINT(S)

The analysis of the primary endpoint will be based on the patient cohort resulting from the 1:1 matching. Time until termination of treatment will be presented for both treatment groups (Dabigatran etexilate vs. VKA) by Kaplan-Meier estimates and displayed graphically, respectively. Especially for time points 3, 6, 9 and 12 months Kaplan-Meier estimates for persistence will be calculated.

The comparison of persistence between the treatments with dabigatran etexilate versus VKA will be conducted by means of the stratified Log-rank test, which takes dependencies resulting from the matching of the treatment groups into account. Patients who discontinue

study prematurely and without documented treatment discontinuation will be censored at study termination. Patients completing the study as planned will be censored at the day after last visit, if no earlier treatment discontinuation is documented. Association between patient characteristics (incl. method of treatment) and persistence will be determined by means of cox regression (univariate and multivariate model). First, univariate regression for each of the independent variables will be performed. Afterwards, all covariates will be entered into a stepwise multivariate regression. The entry level will be $p=0.5$ and the stay level $p=0.1$. Baseline characteristics will be presented stratified by patients who discontinued the study prematurely versus no discontinuation.

A multivariate Cox Regression model (including factors for the calculation of the propensity score and the choice of treatment) will be used as sensitivity analysis. All patients, who are within the “common support” of the empiric PS density function (instead of the matched pairs), will be included in this analysis. The “common support” will be determined after patients with a propensity score above the 97.5% percentile and below the 2.5% percentile have been excluded for each treatment group, respectively. This will be done to avoid high influence of patients with extreme PS.

The following covariates will be used –depending on the sample size- for the Propensity Score Matching and the sensitivity analysis

- CHA₂DS₂-VASC Score (<2, ≥ 2)
- HAS BLED-Score (<3, ≥ 3)
- Age at registration (<65, 65-<75, ≥ 75)
- Previous stroke (Yes, No)
- Treatment (VKA, Pradaxa[®]) (sensitivity analysis only)

and the following covariates will be used –depending on the sample size- for the Cox regression

- CHA₂DS₂-VASC Score (<2, ≥ 2)

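### The matching score has so few distinct values that almost every 1:1 match is a tie, so the pair-stratified log-rank test depends on an unstated tie-break and loses power

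*SAP*

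**What the plan says.** SAP section 7 plans that dabigatran and VKA patients "will be matched 1:1 based on the Exposure Propensity Score (PS) and caliper matching with caliper of width equal to 0.2xStandard deviation of PS". The score comes from a logistic model for treatment choice. SAP section 7 speaks in general of all baseline variables with an a priori association to persistence and adherence; SAP 7.4 then supplies the list: "The following covariates will be used –depending on the sample size- for the Propensity Score Matching and the sensitivity analysis". The list has four items for matching: CHA2DS2-VASc cut at 2, HAS-BLED cut at 3, age in three bands, and previous stroke yes or no. None is continuous.

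For the primary endpoint, SAP 7.4 says: "The comparison of persistence between the treatments with dabigatran etexilate versus VKA will be conducted by means of the stratified Log-rank test", adding that the test allows for the dependence created by matching. Protocol 7.3 says the same. Neither document names the stratum; the matched pair is the natural reading. Neither gives a matching algorithm, processing order, tie-break, seed or replacement rule.

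The amended sample-size section (Protocol, Local Amendment 1, Change 3) assumes 800 patients per drug "with 66% of VKA patients with a matching partner in the dabigatran etexilate group", hence 1056 matched patients. It states power of 97.8%, 84.8% and 61.1% for VKA persistence of 51%, 53.8% and 56.5% against 63% on dabigatran.

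SAP 7.4 also plans a Cox model on the common-support population, without pairs, as a sensitivity analysis. Protocol section 7 and SAP section 7 call all analyses descriptive.

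**The concern.** Pair matching on a propensity score works as intended when the score is fine enough for each patient to have an identifiable nearest neighbour. Here a patient typically shares the exact score with dozens of others. The caliper then decides almost nothing. Within a tied group the program must choose which surplus patients to drop and which partner each remaining patient gets, and the plan does not say how.

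The pair-stratified log-rank test is sensitive to that choice. With two patients per stratum it reduces to a sign test on who stopped first in each informative pair, so re-pairing the same patients changes the answer. Two programmers who follow the SAP faithfully could report different p-values for the primary comparison from one database. The test also ignores all comparisons between patients in different pairs of the same covariate cell, which costs power.

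**Working it through.** **1. Number of score values.** Nominal combinations: 2 × 2 × 3 × 2 = 24. If age 75 and over and stroke each score 2 points (read from the subscripts in the score's name; the documents do not write out the weights), a CHA2DS2-VASc below 2 cannot occur with either. That removes 6 cells with stroke (3 age bands × 2 HAS-BLED levels) and 2 without stroke at age 75 and over, leaving 24 less 8, which is 16. SAP 6.6 keeps missing values as a category; if that enters the score model, up to 66 cells (age complete) or 90 are possible.

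Dividing 1600 patients by the number of cells gives an average of 100 per cell with 16 cells, about 67 with 24 and about 18 with 90. In simulated cohorts of 800 per drug with 16 cells, 96 to 97% of matched pairs had exactly equal scores.

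**2. The plan's own figures.** Matched patients: 2 × 0.66 × 800 = 1056, as stated (528 pairs).

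Power, assuming exponential stopping and 15% exponential drop-out at one year:
- Rates: λ_D = −ln 0.63 = 0.462, λ_V = −ln(VKA persistence), ε = −ln 0.85 = 0.163.
- Event probability: f(λ) = λ/(λ+ε) × [1 − exp(−(λ+ε))].
- Schoenfeld power: Φ(|ln(λ_D/λ_V)| √d / 2 − 1.96), with d = 528 × [f(λ_D) + f(λ_V)].
- At 56.5%: λ_V = 0.571, f(λ_D) = 0.344 and f(λ_V) = 0.405. Their sum is 0.748 before rounding, so d = 528 × 0.748 = 395. With a log hazard ratio of 0.212 and √d = 19.9, half their product is 2.103 before rounding; less 1.96 this is 0.143, and Φ(0.143) = 55.7%.

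The three results are 97.2%, 84.4% and 55.7%. The first two reproduce the stated figures; 61.1% does not. This formula treats the patients as unpaired.

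**3. Power of the pair-stratified test.**
- Share of informative pairs: q = (λ_D+λ_V)/T × (1 − e^−T), with T = λ_D + λ_V + 2ε.
- Informative pairs: m = 528q.
- Probability that the VKA member stops first: π = λ_V/(λ_D+λ_V).
- Power: Φ[(|2π−1|√m − 1.96) / (2√(π(1−π)))].
- At 56.5%: T = 1.358, q = 0.565, m = 298 and π = 0.553. Then |2π−1|√m = 0.105 × 17.3 = 1.82, which less 1.96 is −0.14. The denominator is 0.994, so power is Φ(−0.14) = 44%.

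| VKA persistence | Stated | Unpaired formula, 1056 patients | Informative pairs of 528 | Pair-stratified, formula |
|---|---|---|---|---|
| 51% | 97.8% | 97.2% | 315 | 91% |
| 53.8% | 84.8% | 84.4% | 307 | 73% |
| 56.5% | 61.1% | 55.7% | 298 | 44% |

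Simulation with 34% dropped gave 90%, 73% and 41% for the pair-stratified test. A log-rank test stratified on cells gave about 96%, 86% and 57% within the matched set, and 99.8%, 93% and 67% with all patients. Type I error was near 5% for the pair-stratified test and for the all-patient cell-stratified test.

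**4. Dependence on the tie-break.** Each simulated data set was held fixed and re-matched many times (16 cells, random tie-breaks within cells):

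| Dropped per arm | SD of z over tie-breaks | Data sets with 10% to 90% of tie-breaks significant, VKA 56.5% | Same, VKA 53.8% |
|---|---|---|---|
| 34% | 0.62 | 68% | 55% |
| 22% | 0.58 | 65% | 44% |
| 11% | 0.53 | 57% | 30% |

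A separate simulation with greedy nearest-neighbour caliper matching gave SDs of 0.52 to 0.62 with 13 to 35% dropped per arm. Under a criterion of 5% to 95%, 25 to 70% of its data sets were order-dependent. With nobody dropped and only the pairing changed, the SD of z was still 0.46.

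One data set as an example (63% vs 53.8%, strong imbalance): median p 0.11, central 95% of orders 0.005 to 0.59, and 25% of orders at or below 0.05. The cell-stratified test on all its patients gives a single value, p = 0.028.

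**5. What dropping tied patients achieves.** Take two cells with a mix of 67% and 33% in one arm and the reverse in the other. Matching keeps 0.33 × 800 = 264 per arm in each cell: 528 per arm, or 66%. The matched arms are then split equally between the cells, so the marginal Kaplan-Meier curves become comparable on these covariates. Once the comparison is made within cells, the dropped patients add information and no imbalance.

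**The case against.** The best defence is that little hangs on this p-value. The primary endpoint is the 12-month Kaplan-Meier persistence per drug. Pairing does not alter those curves, though the choice of whom to drop can. There is no confirmatory hypothesis, no error control, and no stated decision at 0.05. The Cox sensitivity analysis uses the same four covariates and does not depend on matching order. All of this stands, and it limits the severity. It does not remove the order dependence of the planned between-drug test, for which the protocol itself reports power at p ≤ 0.05.

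Several stronger readings are tempting but not supported:
- **At most 16 values.** This needs 2-point weights that the documents do not spell out, and complete data. The abbreviation lists also say over 75, whereas the SAP band is 75 and over. A missing level would add cells, though 1600 patients would still be heavily tied.
- **A third of patients are lost because of this score.** The 34% is a planning assumption carried over from before the amendment. The actual loss depends on imbalance between the arms; the instability is present at 11% and 22% too.
- **Dropping tied patients brings no balance.** It does balance the marginal curves (step 5). It is superfluous only once the test is stratified by cell.
- **The result cannot be reproduced.** A stored program with a fixed order reproduces itself. What is missing is a pre-specified order, and a fixed seed would not recover the lost power.

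A reader could also point to SAP section 7's broader statement about baseline variables. Since SAP 7.4 gives the explicit list, and allows for using less of it, that sentence does not make the score finer.

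**Conclusion.** The concern holds in this form and should be fixed; it does not invalidate the study. The score is coarse enough that nearly all matches are exact ties, and the pair-stratified test varies with an unstated tie-break by an SD of z of about 0.5 to 0.6. In roughly 30 to 70% of simulated data sets at VKA persistence 53.8 to 56.5%, the tie-break settles which side of 0.05 the result falls on. Power with 528 pairs is about 90/73/42%, below the stated 97.8/84.8/61.1%. At 56.5% about 5 of the missing points are not due to pairing, because 61.1% does not reproduce even unpaired.

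Assumptions: strata are matched pairs; the SAP 7.4 list is the full list; stopping and drop-out are exponential; cell sizes and cell risks are assumed. The simulated figures show direction and order of magnitude, while the pair-stratified power also follows from the formula in step 3.

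**What to change.** Replace pairs by covariate cells (or tied score values) as strata of the log-rank test, and use all FAS patients in cells that contain both drugs. Give Kaplan-Meier curves standardised to a named common cell mix, for example that of all patients in the overlapping cells. Keep the 1:1 matched analysis as a sensitivity analysis with a stated algorithm, patient order and stored seed. Record the change in SAP section 4, which now lists none.

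If the matched set must stay primary, stratify on cells within it. That recovers much of the power (about 96/86/57%) and removes the dependence on who is paired with whom. Which surplus patients are kept would still need a stated order and seed.

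Cost: SAP wording and a short program change, with no new data. The comparison population becomes the overlap of both arms rather than a matched subset, and the primary analysis departs from the 1:1 matching in protocol 4.1.2 and 7.3, which has to be acknowledged.
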